9.1.1 Treatment Phase

During the Treatment Phase, subjects still on treatment will continue the same treatment they received upon discontinuation of the parent study. Subjects will remain on treatment in consecutive cycles as per the parent study protocol until disease progression, development of unacceptable toxicity, subject request, withdrawal of consent, discontinuation of Study E7080-G000-604 by the sponsor, use of non-permitted concomitant drugs, unacceptable non-compliance with the protocol, or if the subject is lost to follow-up.

9.2 Discussion of Study Design, Including Choice of Control Groups

Subjects will enter the study at the same doses of study drug of lenvatinib or the combination regimen, or any other comparator therapy (except placebo), upon discontinuation of the parent study. This is a roll-over open-label study with no control group.

9.3 Selection of Study Population

It is expected that approximately 50 subjects will be initially rolled over to the study. It is anticipated that additional subjects may also roll over to the study in the future. Subjects who meet all of the inclusion criteria and none of the exclusion criteria, with no evidence of progressive disease, and who have tolerated study drug(s) in their parent study without significant toxicities will be rolled over to this study. Subjects with evidence of disease progression but who continue to derive clinical benefit as determined by the investigator would require discussion with the sponsor on an individual case-by-case basis prior to enrollment in this study.

9.3.1 Inclusion Criteria

It is required for all subjects currently participating in other lenvatinib studies to meet the following eligibility criteria prior to entry in the study.

1. Provide signed written informed consent for the roll-over study

- 2. Currently enrolled in an Eisai sponsored lenvatinib clinical study and still receiving at least one of the study drugs from that protocol
- 3. Currently deriving clinical benefit from at least one of the study drug(s) as determined by the investigator
- 4. Must be able and willing to comply with the current roll-over protocol requirements
- 5. Continued ability to swallow and retain orally administered study drug(s)
- 6. Does not have any clinically significant gastrointestinal abnormalities that may alter absorption such as malabsorption syndrome or major resection of the stomach or bowels
- 7. Women of childbearing potential and men with reproductive potential (if specified by the parent study) must be willing to continue to use highly effective methods of contraception control as per local practices of standard of care during the period of the study
- 8. Women of childbearing potential must have a negative serum pregnancy test at the time of transition to the study and before continuing study drug(s).

9.3.2 Exclusion Criteria

Subjects who meet any of the following criteria will be excluded from this study:

- 1. Permanent discontinuation of study drug(s) in the parent study due to toxicity or disease progression and without clinical benefit
- 2. Receiving any prohibited medication(s) as described in the parent study
- 3. Have any unresolved toxicity that meets the criteria for study drug(s) discontinuation or withdrawal criteria from the parent study at the time of transition to this study
- 4. Uncontrolled diabetes, hypertension or other medical conditions at the time of transition to the roll-over study that may interfere with assessment of toxicity
- 5. Pregnant or lactating female
- 6. Any serious and/or unstable pre-existing medical condition, psychiatric disorder or other conditions at the time of transition to the roll-over study that could interfere with subject's safety in the opinion of the investigator

9.3.3 Removal of Subjects From Therapy or Assessment

The investigator may discontinue treating a subject with study treatment or withdraw the subject from the study at any time for safety or administrative reasons. The subject may decide to discontinue study treatment or withdraw from the study at any time for any reason. The reason for discontinuation will be documented. If a subject withdraws consent, the date will be documented in the CRF and source documents.

9.4 Treatment(s)

9.4.1 Treatment(s) Administered

Subjects enrolled from parent study will enter the roll-over study and will continue the study drug of lenvatinib, or combination regimen, or any other comparator therapy (except placebo) at the same doses upon discontinuation of the parent study. Study drug(s) administered will be recorded in the case report form (CRF).

Subject must not be dispensed more than a 3-months supply of study drug(s) at any particular time during participation in Study E7080-G000-604.

For China Only:

Comparator Drug: Sorafenib

The subject(s) who receive the comparator in the parent study will be enrolled to Cohort C. In the event that comparator clinical supply is limited, the comparator treatment may be obtained commercially from local sources and reimbursed by the sponsor unless this is prohibited by specific country laws. Further instructions on acquisition procedures for commercial supply will be provided by the sponsor.

Criteria for Interruption of Treatment, Dose Reduction and Resumption

Dose reduction and interruptions for subjects who experience toxicity will be made according to the guidelines provided in the parent protocol.

9.4.1.1 Management of Toxicities

Management of toxicities including hypertension, proteinuria, hepatotoxicity, thromboembolic events, Posterior Reversible Encephalopathy Syndrome/ Reversible Posterior Leukoencephalopathy Syndrome and hypocalcemia and any other adverse events will be according to the parent study.

9.4.1.2 Chemical Name, Structural Formula of Lenvatinib

- Test drug code: E7080
- Generic name: lenvatinib, lenvatinib mesilate, lenvatinib mesylate
- Chemical name: 4-[3-Chloro-4-(N'-cyclopropylureido)phenoxy]-7-methoxyquinoline-6-carboxamide methanesulfonate
- Molecular formula: C₂₁H₁₉ClN₄O₄•CH₃SO₃H
- Molecular weight: 522.96
- Structural formula: (see Figure 2)

Figure 2Structural Formula of Lenvatinib Mesilate

9.4.1.3 Chemical Name, Structural Formula of Study Drug in Combination Regimen other than Lenvatinib

The following information if applicable will be provided in the corresponding parent study.

9.4.1.4 Prior and Concomitant Therapy

Any medication that is considered necessary for the subject's health and that is not expected to interfere with the evaluation of or interact with lenvatinib or with the lenvatinib combination regimen as per the parent study may be continued during the study.

Treatment of complications or AEs, or therapy to ameliorate symptoms (including blood products, blood transfusions, fluid transfusions, antibiotics, and antidiarrheal drugs), may be given at the discretion of the investigator, unless it is expected to interfere with the evaluation of (or to interact with) lenvatinib.

If a subject is receiving treatment with lenvatinib and requires surgery during the study, the stop time and restart time of lenvatinib should be as follows:

- For minor procedures: stop lenvatinib at least 2 days before the procedure and restart it at least 2 days after, once there is evidence of adequate healing and no risk of bleeding.
- For major procedures: stop lenvatinib at least 1 week (5 half-lives) prior to surgery and then restart it at least 1 week after, once there is evidence of adequate healing and no risk of bleeding.

Aspirin, nonsteroidal anti-inflammatory drugs (NSAIDs), and low-molecular-weight heparin (LMWH) are permissible but should be used with caution. Granulocyte colony-stimulating factor (g-CSF) or equivalent may be used in accordance with American Society of Clinical Oncology (ASCO), institutional, or national guidelines. Erythropoietin may be used according to ASCO, institutional, or national guidelines, but the subject should be carefully monitored for increases in red blood cell (RBC) counts.

If concomitant medication/therapy is administered for an AE, investigators will record that AE on the Adverse Event CRF.

9.4.1.5 Drug-Drug Interactions

Lenvatinib's weak in vitro inhibitory and induction potential on cytochrome P450 enzymes (CYP P450) (Study No. XT063020) suggests a low risk of lenvatinib interference with the PK of other drugs metabolized by CYP P450 enzymes which are co-administered in usual clinic practice. Nonclinical studies identify CYP3A4 as the important CYP isozyme responsible for human hepatic metabolism of lenvatinib. However, clinical studies conducted showed that co-administration of lenvatinib with CYP3A4/P-glycoprotein (P-gp) inhibitors or inducers is not of clinical concern. The main metabolic pathways for lenvatinib in humans were identified as enzymatic (CYP3A and aldehyde oxidase) and non-enzymatic processes (LENVIMA[®] Package Insert). Please refer to Appendix 1 and http://medicine.iupui.edu/clinpharm/ddis/ for the most current information.

For subjects receiving everolimus, drugs or substances (including herbal supplements or grapefruit juice) known to be potent inhibitors of CYP3A4/P-gp should not be used. Potent inducers of CYP3A4/P-gp should not be used unless there is no alternative treatment available. Moderate/ weak inhibitors or inducers or substrates of CYP3A4 and/or P-gp should be used with caution. Dose reduction of everolimus may be considered when coadministering moderate CYP3A4 or P-gp inhibitors. For further information please refer to the prescribing information. No formal pharmacokinetic drug interaction studies have been conducted with pembrolizumab. Pembrolizumab is a monoclonal antibody; pharmacokinetic interactions with lenvatinib (and vice-versa) are not expected. Strong CYP3A4 inhibitors such as ketoconazole may increase sunitinib plasma concentrations. CYP3A4 inducers such as rifampin may decrease sunitinib plasma concentrations. Selection of an alternate concomitant medication with no or minimal enzyme inhibition or induction is recommended. A dose reduction for sunitinib to a minimum of 37.5 mg daily should be considered if sunitinib must be co-administered with a strong CYP3A4 inhibitor. A dose increase for sunitinib to a maximum of 87.5 mg daily should be considered if sunitinib must be co-administered with a CYP3A4 inducer. If dose is increased, the patient should be monitored carefully for toxicity. In regards, to lenvatinib combination regimen, please refer to drug-drug interactions section in the parent study.

9.4.1.6 Prohibited Concomitant Therapies and Drugs

The following therapies are prohibited during the study:

- Concurrent other anticancer therapies such as chemotherapy, tyrosine-kinase inhibitor (TKIs), antitumor interventions (surgical resection, surgical de-bulking of tumors, etc.), or cancer immunotherapy
- Radiotherapy except for palliative radiotherapy: palliative radiotherapy of painful pre-existing non-target bone metastases will be permitted without being considered progressive disease
- Concurrent other investigational drugs

If subjects receive antitumor therapies listed above, or any additional antitumor therapies, this will be judged to represent evidence of disease progression, and study medication will be discontinued.

9.4.2 Treatment Compliance

Records of treatment compliance for each subject will be kept during the study. Clinical research associates (CRAs) will review treatment compliance during site visits and at the completion of the study.

9.4.3 Drug Supplies and Accountability

In compliance with local regulatory requirements, drug supplies will not be sent to the investigator (or if regionally required, the head of the medical institution or the designated pharmacist) until the following documentation has been received by the sponsor:

- A signed and dated confidentiality agreement
- A copy of the final protocol signature page, signed and dated by both the sponsor and investigator
- Written proof of approval of the protocol, the ICFs, and any other information provided to the subjects by the IRB/IEC for the institution where the study is to be conducted
- A copy of the IRB/IEC-approved ICF and any other documentation provided to the subjects to be used in this study
- The IRB/IEC membership list and statutes or Health and Human Services Assurance number
- An investigator-signed and dated Food and Drug Administration (FDA) Form FDA 1572, where applicable
- Financial Disclosure form(s) for the principal investigator (PI) and all sub-investigators listed on Form FDA 1572, where applicable
- A signed and dated curriculum vitae (CV) of the PI including a copy of the PI's current medical license or medical registration number on the CV
- A signed and dated clinical studies agreement

The investigator and the study staff (or if regionally required, the head of the medical institution or the designated pharmacist) will be responsible for the accountability of all study drugs (dispensing, inventory, and record keeping) following the sponsor's instructions and adherence to Good Clinical Practice (GCP) guidelines as well as local or regional requirements.

Study drug(s) dispensed (Kit #) will be recorded in the CRF.

Under no circumstances will the investigator allow the study drugs to be used other than as directed by this protocol. Study drugs/study supplies will not be dispensed to any individual who is not enrolled in the study. The site must maintain an accurate and timely record of the

following: receipt of all study drugs, dispensing of study drugs to the subject, collection and reconciliation of unused study drugs that are either returned by the subjects or shipped to site but not dispensed to subjects, and return of reconciled study drugs to the sponsor or (where applicable) destruction of reconciled study drugs at the site. This includes, but may not be limited to:(a) documentation of receipt of study drugs, (b) study drugs dispensing/return reconciliation log, (c) study drugs accountability log, (d) all shipping service receipts, (e) documentation of returns to the sponsor, and (f) certificates of destruction for any destruction of study drug that occurs at the site. All forms will be provided by the sponsor.

The study drugs and inventory records must be made available, upon request, for inspection by a designated representative of the sponsor or a representative of a health authority (eg. FDA, Medicines and Healthcare Products Regulatory Agency [MHRA]). As applicable, all unused study drugs and empty and partially empty blister packages from used study drugs are to be returned to the investigator (or if regionally required, the head of the medical institution or the designated pharmacist) by the subject and, together with unused study drugs that were shipped to the site but not dispensed to subjects, are to be returned to the sponsor's designated central or local depot(s) during the study or at the conclusion of the study, unless provision is made by the sponsor for destruction of study drugs and containers at the site. Destruction at the site will only occur under circumstances where regulation or supply type prohibits the return of study drugs to the central or local depot(s). Approval for destruction to occur at the site must be provided by the sponsor in advance. Upon completion of drug accountability and reconciliation procedures by the site's personnel and documentation procedures by the sponsor's personnel, study drugs that are to be returned to the sponsor's designated central or local depot(s) must be boxed, sealed, and shipped back to the central or local depot(s) following all local regulatory requirements. In some regions, study drugs may be removed from the site and hand delivered to the central or local depot by sponsor representatives. Where study drugs are approved for destruction at the site, destruction will occur following the site's standard procedures and certificates of destruction will be provided to the sponsor. Drug accountability will be reviewed during site visits and at the completion of the study.

9.5 Study Assessments

9.5.1 Demography

Subject demography information will be collected and recorded in the CRF. Demography information includes age, sex, and race/ethnicity.

9.5.2 Medical History and Physical Examinations

Initial physical examination and any therapeutic area-specific assessments will be performed as per local standard of care or as clinically indicated.

9.5.3 Efficacy Assessments

Tumor assessments will be performed as per local standard of care .

9.5.4 Pharmacokinetic, Pharmacodynamic, Pharmacogenomic, and Other Biomarker Assessments

Not applicable.

9.5.5 Pharmacokinetic Assessments

Not applicable.

9.5.6 Pharmacodynamic, Pharmacogenomic, and Other Biomarker, Assessments

Not applicable.

9.5.7 Safety Assessments

Safety assessments will consist of monitoring and recording all TEAEs, including all Common Terminology Criteria for Adverse Events (CTCAE) v4.03 grades (for both increasing and decreasing severity), and SAEs. Long term safety information will be collected at the time drug is dispensed to the subject.

Monitoring of hematology, blood chemistry, and urine values; measurement of vital signs and performance of physical examinations should be performed per local standard of care or as clinically indicated

9.5.7.1 Adverse Events

An adverse event (AE) is any untoward medical occurrence in a patient or clinical investigation subject administered an investigational product. An AE does not necessarily have a causal relationship with the medicinal product. For this study, the study drug(s) is/are lenvatinib, or lenvatinib combination regimen, or any other comparator therapy (except placebo) as per the parent study.

AEs collected in this study must be treatment-emergent adverse events (TEAE). This is defined as an AE that emerges during treatment in the roll-over study, having been absent before the time the subject signs the roll-over study ICF or

- Re-emerges during treatment in the roll-over study, having been present before signing the ICF but stopped before signing the ICF, or
- Worsens in severity during treatment in the roll-over study relative to the pre-ICF state, when the AE is continuous.

The criteria for identifying TEAEs in this study are:

- Any unfavorable and unintended sign (including an abnormal laboratory finding), symptom, or disease temporally associated with the use of an investigational product, whether or not considered related to the investigational product
- Any new disease or exacerbation of an existing disease.

- Any deterioration in nonprotocol-required measurements of a laboratory value or other clinical test (eg, ECG or x-ray) that results in symptoms, a change in treatment, or discontinuation of study drug
- Recurrence of an intermittent medical condition (eg, headache) not present pretreatment (Baseline)
- An abnormal laboratory test result should be considered a TEAE if the identified laboratory abnormality leads to any type of intervention, withdrawal of study drug, or withholding of study drug, whether prescribed in the protocol or not

A laboratory result should be considered by the investigator to be a TEAE if it:

- Results in the withdrawal of study drug
- Results in withholding of study drug pending some investigational outcome
- Results in an intervention, based on medical evaluation (eg, potassium supplement for hypokalemia
- Results in any out-of-range laboratory value that in the investigator's judgment fulfills the definitions of a TEAE with regard to the subject's medical profile
- Increases in severity compared to the pre-ICF state by 2 or more CTCAE grades (Table 1 and Appendix 2 for CTCAE v4.03), with the exception of lymphocytes, albumin, cholesterol, glucose, and phosphate. For these tests, any change of 2 or more grades will be evaluated by the investigator to determine if it is of clinical significance and, if so, will be considered a TEAE

All TEAEs and SAEs, regardless of relationship to study drug or procedure, should be recorded beginning from the time the subject signs the roll-over study ICF for up to 28 days after the last dose of study drug(s) (or $5 \times$ half-life of study drug[s], whichever is longer).

Abnormal laboratory values should not be listed as separate AEs if they are considered to be part of the clinical syndrome that is being reported as a TEAE. It is the responsibility of the investigator to review all laboratory findings in all subjects and determine if they constitute a TEAE. Medical and scientific judgment should be exercised in deciding whether an isolated laboratory abnormality should be classified as a TEAE. Any laboratory abnormality considered to constitute a TEAE should be reported on the Adverse Event CRF.

Abnormal ECG (QTcF) results, if not otherwise considered part of a clinical symptom that is being reported as a TEAE, should be considered a TEAE if the QTcF interval is more than 450 ms and there is an increase of more than 60 ms from baseline. Any ECG abnormality that the investigator considers as a TEAE should be reported as such.

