Note: Subjects will be permitted to continue study drug(s) beyond initial disease progression as long as investigator-assessed clinical benefit is observed after discussion and approval by the sponsor and if the subject is tolerating study drug(s). Subjects will discontinue study drug(s) upon evidence of further progression and/or loss of clinical benefit as judged by the investigator

- Unacceptable toxicity
- Subject request
- Withdrawal of consent
- Termination of the study by sponsor
- Use of non-permitted concomitant drug(s)
- Unacceptable non-compliance with the protocol
- Lost to follow-up

Concomitant Drug/Therapy

Any medication which is considered necessary for the subject's welfare, and which is not expected to interfere with the evaluation of the investigational product, may be given at the discretion of the investigator.

The concomitant therapies that are permitted and prohibited therapies that are not allowed during the study will be in accordance with the local prescribing information and/or investigator brochure for study drug(s).

The following therapies are prohibited during the study:

- Concurrent other anticancer therapies such as chemotherapy, tyrosine-kinase inhibitor (TKIs), antitumor interventions (surgical resection, surgical de-bulking of tumors, etc.), or cancer immunotherapy
- Radiotherapy except for palliative radiotherapy: palliative radiotherapy of painful pre-existing non-target bone metastases will be permitted without being considered progressive disease
- Concurrent other investigational drugs

If subjects receive antitumor therapies listed above, or any additional antitumor therapies, this will be judged to represent evidence of disease progression, and study medication will be discontinued.

Assessments

Efficacy Assessments

Only disease progression will be recorded in the study case report forms (CRFs).

Pharmacokinetic Assessments

Not applicable

Pharmacodynamic, Pharmacogenomic, and Other Biomarker Assessments

Not applicable

Safety Assessments

Safety assessments will consist of monitoring and recording all TEAEs and SAEs using Common Terminology Criteria for Adverse Events (CTCAE) v4.03. Long term safety information will be collected at the time drug is dispensed to the subject.

Safety Reporting Requirements

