9.5.7.4 Serious Adverse Events and Events Associated with Special Situations

A serious adverse event (SAE) is any untoward medical occurrence that at any dose:

- Results in death
- Is life-threatening (ie, the subject was at immediate risk of death from the adverse event as it occurred; this does not include an event that, had it occurred in a more severe form or was allowed to continue, might have caused death)
- Requires inpatient hospitalization or prolongation of existing hospitalization
- Results in persistent or significant disability/incapacity
- Is a congenital anomaly/birth defect (in the child of a subject who was exposed to the study drug)

Other important medical events that may not be immediately life-threatening or result in death or hospitalization but, when based on appropriate medical judgment, may jeopardize the subject or may require intervention to prevent one of the outcomes in the definition of SAE listed above should also be considered SAEs. Medical and scientific judgment should be exercised in deciding whether expedited reporting is appropriate in such situations.

In addition to the above, events associated with special situations include pregnancy or exposure to study drug(s) through breastfeeding; TEAEs associated with study drug overdose, misuse, abuse, or medication error. These events associated with special situations are to be captured using the SAE procedures but are to be considered as SAEs only if they meet one of the above criteria. All TEAEs associated with special situations are to be reported on the CRF whether or not they meet the criteria for SAEs.

All SAEs must be followed to resolution or, if resolution is unlikely, to stabilization.

The following hospitalizations are not considered to be SAEs because there is no "adverse event" (ie, there is no untoward medical occurrence) associated with the hospitalization:

- Hospitalizations for respite care
- Planned hospitalizations required by the protocol
- Hospitalization planned before informed consent (where the condition requiring the hospitalization has not changed after study drug administration)
- Hospitalization for administration of study drug(s) or insertion of access for administration of study drug(s)
- Hospitalization for routine maintenance of a device (eg, battery replacement) that was in place before study entry.

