9.5.8 Schedule of Procedures/Assessments

9.5.8.1 Schedule of Procedures/Assessments

All assessments for efficacy and safety will be performed as per local standard of care or as clinically indicated.

- 9.5.9 Reporting of Serious Adverse Events, Pregnancy, and Events Associated with Special Situations
- 9.5.9.1 Reporting of Serious Adverse Events

All SERIOUS ADVERSE EVENTS, regardless of their relationship to study treatment, must be reported on a completed SAE form by email or fax as soon as possible but no later than 24 hours from when the investigator becomes aware of the event.

Serious adverse events, regardless of causality assessment, must be collected as indicated in the parent protocol.

Regardless of treatment arm, all SAEs must be followed to resolution or, if resolution is unlikely, to stabilization. Any SAE judged by the investigator to be related to the study treatment or any protocol-required procedure should be reported to the sponsor regardless of the length of time that has passed since study completion.

The detailed contact information for reporting of SAEs is provided in the Investigator Study File.

For urgent safety issues, please ensure all appropriate medical care is administered to the subject and contact the appropriate study team member listed in the Investigator Study File.

It is very important that the SAE report form be filled out as completely as possible at the time of the initial report. This includes the investigator's assessment of causality.

Any follow-up information received on SAEs should be forwarded within 24 hours of its receipt. If the follow-up information changes the investigator's assessment of causality, this should also be noted on the follow-up SAE form.

Preliminary SAE reports should be followed as soon as possible by detailed descriptions including copies of hospital case reports, autopsy reports, and other documents requested by the sponsor.

The investigator must notify his/her IRB/IEC of the occurrence of the SAE in writing, if required by their institution. A copy of this communication must be forwarded to the sponsor to be filed in the sponsor's Trial Master File.

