6.1.3 Efficacy Assessments

Tumor assessments will be performed as per local standard of care. Results of these assessments will not be recorded in the eCRF and will not be summarized.

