6.5.2 Adverse Events

The adverse event (AE) verbatim descriptions (investigator terms from the eCRF) will be classified into standardized medical terminology using the Medical Dictionary for Regulatory

Activities (MedDRA). The linked MedDRA preferred term (PT) and primary system organ class (SOC) are also captured in the database.

AEs collected in this study must be treatment-emergent adverse events (TEAE). This is defined as an AE that emerges during treatment in the rollover study, having been absent before the time the subject signs the rollover study ICF or

- Re-emerges during treatment in the rollover study, having been present before signing the ICF but stopped before signing the ICF, or
- Worsens in severity during treatment in the rollover study relative to the pre-ICF state, when the AE is continuous.

Only those AEs that are treatment emergent will be included in summary tables. TEAEs are those occurring on or after the first dose date of study drug and on or before 28 days after the last dose of study drug. All TEAEs will be presented in subject data listings.

An overview table, including the number and percentage of subjects with TEAEs, SAEs, deaths, and those with TEAEs that led to study drug discontinuation, interruption, or dose reduction will be provided. The number (percentage) of subjects with TEAEs will be summarized by SOC and PT, by relationship to study drug (Yes [related] and No [not related]), and by CTCAE toxicity grade as follows:

- Overview of TEAEs
- TEAEs by SOC and PT
- TEAEs by decreasing frequency of PT
- TEAEs with CTCAE Grade ≥ 3 by decreasing incidence of PT
- Treatment-emergent serious AEs by decreasing incidence of PT
- Overview of treatment-related TEAEs
- Treatment-related TEAEs by SOC and PT
- Treatment-related TEAEs by decreasing frequency of PT
- Treatment-related TEAEs with CTCAE Grade ≥ 3 by decreasing incidence of PT
- Treatment-related treatment-emergent serious AEs by decreasing incidence of PT
- Fatal TEAEs by decreasing incidence of PT
- TEAEs leading to treatment discontinuation of lenvatinib

The following listings will be provided for the subjects in the Safety Analysis Set:

- Demographics

- Disposition
- Lenvatinib dosing
- All AEs
- All SAEs
- Adverse events with CTCAE Grade 3 or above
- All AEs leading to study drug discontinuation
- All fatal AEs

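### No rule says whether progression of the study cancer is a TEAE, and the criteria as worded let it into the all-cause serious, fatal and discontinuation outputs

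*Protocol*

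**What the plan says.** Protocol Section 9.5.7.1 starts from a broad definition: "An adverse event (AE) is any untoward medical occurrence in a patient or clinical investigation subject administered an investigational product". Its criteria for identifying TEAEs include "Any new disease or exacerbation of an existing disease", with no carve-out for the underlying malignancy. Cause does not filter events at entry: "All TEAEs and SAEs, regardless of relationship to study drug or procedure, should be recorded". Section 9.5.7.4 makes death and inpatient hospitalization serious, and its exceptions cover only certain kinds of hospitalization.

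Progression also has its own track. Under efficacy assessments the Synopsis says "Only disease progression will be recorded in the study case report forms (CRFs". Section 9.5.10 lists progression and unacceptable toxicity as different reasons for stopping, and allows more than one reason per subject. SAP Section 6.2.2 tabulates reasons by eCRF category.

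On output, SAP Section 6.5.2 plans an overview table, treatment-emergent SAEs by preferred term, "Fatal TEAEs by decreasing incidence of PT", and a table of TEAEs that ended lenvatinib. Protocol Section 9.7.1.6 adds time to stopping treatment because of a TEAE. None of these mentions progression terms. SAP Section 4 presents results for China, Rest of World and all subjects.

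**The concern.** Long-term safety is the only objective, so the serious, fatal and discontinuation tables are the main product of the study. If some sites record progression of the cancer as an adverse event, those all-cause rates mix the course of the disease with the toxicity of the drug. If sites or parent studies differ in practice, a difference between the China and Rest of World columns could reflect recording habit rather than safety.

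No other planned summary would resolve this. There is no efficacy analysis, and of tumor assessments SAP Section 6.1.3 says "Results of these assessments will not be recorded in the eCRF and will not be summarized". That sentence says nothing about how adverse events are coded. It matters only because it leaves the disposition table as the one planned summary that shows progression as such. Treatment may continue past a first progression (Synopsis; Section 9.5.10), so disposition will not show every progression either.

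**Working it through.** **1. Can the wording reach progression?** Growth of a cancer present at entry fits the ordinary sense of the criterion quoted from Section 9.5.7.1. A second criterion there covers deterioration in a clinical test outside protocol requirements that leads to stopping study drug. Imaging follows local standard of care (Sections 9.5.3 and 9.5.8.1), so a scan that ends treatment can be read as meeting that criterion too. The wording permits the reading but does not state it.

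**2. Does anything exclude it?**
- Section 9.5.7.1: no exception.
- Section 9.5.7.4: exceptions for some hospitalizations only.
- Section 9.5.9.1: "Serious adverse events, regardless of causality assessment, must be collected as indicated in the parent protocol". This hands SAE collection to documents that are not available here. It covers SAEs, whereas the TEAE criteria are set in this protocol.
- SAP Section 6.5.2: no exclusion of progression terms in any table.

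**3. Which outputs are exposed?** Those that are all-cause: the overview rows, treatment-emergent SAEs, fatal TEAEs, TEAEs leading to discontinuation, and time to discontinuation for a TEAE. The SAP window runs to 28 days after the last dose, so a cancer death soon after stopping can fall inside it. The treatment-related tables are less exposed, because they depend on the investigator's causality answer.

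**4. Size.** The plan has no figure to reproduce: SAP Section 5 reports no formal sample size calculation and expects about 50 subjects initially. The documents give no number of progressions, so the counts below are assumptions.

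The largest increase when k subjects have progression recorded as a TEAE is 100 × k/N. With N = 50:

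| k | Added, percentage points (at most) |
|---|---|
| 1 | 100 × 1/50 = 2 |
| 5 | 100 × 5/50 = 10 |
| 10 | 100 × 10/50 = 20 |
| 20 | 100 × 20/50 = 40 |

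These are maxima because the tables count subjects. A subject who already has a qualifying event in that table adds nothing to its total.

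For fatal TEAEs, assume 2 subjects with other causes (2/50 = 4%) and k progression deaths inside the window, so the rate is 100 × (2 + k)/50:

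| k | Fatal TEAE rate |
|---|---|
| 0 | 4% |
| 1 | 6% |
| 3 | 10% |
| 5 | 14% |
| 10 | 24% |

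Within a regional column of n subjects, each such record adds up to 100/n points. This is more than 2 whenever n is below 50. The documents do not give n.

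**The case against.** The strongest answer is that the documents treat progression as something other than toxicity: it has its own CRF item, its own discontinuation reason and its own disposition category. Protocol Section 9.7 names fatal TEAEs and deaths as separate outputs, which suggests the two were not assumed to coincide. A rule on progression may exist in the parent protocols, to which SAE collection is deferred, or in the CRF Completion Guidelines that Section 9.6.1 makes binding. The SAP also separates part of the problem already. The serious and fatal tables are by preferred term, so a coded progression term would appear as its own row. Fatal events and events leading to discontinuation are listed by subject, and treatment-related events have their own tables.

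Most of this stands, and it limits the point. A reader might infer that progression necessarily enters the tables, or that every subject who stops for progression is also a TEAE discontinuation. No passage says either. Nor is this double counting in a strict sense, since disposition and adverse event tables are not summed.

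What remains is that no sentence in either document turns the separate track into an exclusion. Any rule held elsewhere is not carried into the SAP and could differ between parent studies. Preferred-term rows do not correct the overview totals, and the discontinuation table is not stated to be by preferred term.

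**Conclusion.** The point holds as a missing rule, not as a stated decision to count progression. The criterion as worded permits progression in the all-cause outputs of a safety-only study, and neither document lets a reader tell whether it is there.

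The size cannot be fixed from the documents. It ranges from zero, if sites already exclude progression, up to 2 percentage points per affected subject in a given table, assuming N is about 50 and the subject has no other qualifying event there. A larger enrolment would shrink the per-subject effect.

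A reader might try to size the effect from the Phase 3 thyroid cancer trial in Protocol Section 7, by adding its 14.2% discontinued for adverse events to a progression rate derived from its 18.3-month median PFS. The documents do not support that:
- The 14.2% is a whole-trial proportion (median exposure 13.8 months), not a rate at a fixed time.
- PFS events include deaths and need not end treatment here.
- The roll-over population spans several tumor types and is selected for continuing benefit.

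**What to change.** In SAP Section 6.5.2, define a list of MedDRA preferred terms for progression of the study malignancy and flag them in the adverse event dataset. Present the overview rows, and the tables of treatment-emergent SAEs, fatal TEAEs and TEAEs leading to discontinuation, both including and excluding the flagged terms. Apply the same split to time to discontinuation for a TEAE if that summary is produced. Show deaths and discontinuations due to progression separately.

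The cost is one dataset flag and a few extra rows or tables, with no new data.

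If sites are still recording data, also state one recording rule for progression in Protocol Section 9.5.7.1 or the CRF guidelines, consistent with the parent protocols. SAP version 2.0 is dated 28 Feb 2024 and its introduction describes study conduct in the past tense, so that sentence may come too late to affect much of the data. The tabulation does not depend on it.
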